1. PROBLEM

Anaphylaxis is a condition frequently encountered in emergency departments (0.05 to 2% in the general population)¹, which is defined by a severe allergic reaction that appears quickly and has fatal potential. As a result of an anaphylaxis, a serious phenomenon called a "biphasic reaction" can occur. This reaction is the reappearance of anaphylactic symptoms several hours after treatment.

The diagnosis of anaphylaxis is based on the impairment of more than one system (muco-skin, cardiovascular, respiratory, digestive) and its definition, the most recognized, is based on the NIAID/FAAN² criteria developed in 2006 (Box 1). Because of its severity, the treatment of anaphylaxis requires rapid management, which relies mainly on the administration of epinephrine. Other treatments can also be used. Among other things, antihistamics can decrease skin symptoms; intravenous hydration contributes to hemodynamic stabilization; and intravenous corticosteroids may decrease the likelihood of a biphasic reaction. However, the effectiveness of the latter treatment option remains debated in the literature.

The theoretical risk of rebound reaction, or biphasic reaction, is classically described up to 72 hours after the initial anaphylactic event. The biphasic reaction is defined as a recurrence or occurrence of new signs or symptoms after the resolution of the initial reaction, without re-exposure to the allergen³. The potential occurrence of a biphasic reaction often warrants observation of patients for several hours in emergency departments following the management of the initial anaphylaxis. Although the recommendations and guidelines generally propose observation times of four to six hours, there is no clear consensus or evidence to guide this conduct. It may even be suggested to observe patients up to 24 hours^{4,5,6}. To date, there are no prognostic factors to identify a more at-risk patient who would benefit from such an observation. As these reactions are a relatively rare phenomenon (4 to 5%, but could be as high as 20% according to some sources⁵) and the symptoms observed are usually less significant than at the initial presentation⁷, it is therefore possible that a prolonged observation period is not necessary for some patients who do not have high risk factors for biphasic reaction.

Box 1: NIAID/FAAN ANAPHYLAXIS CRITERIA

Presence of one of three following criteria:

1. Sudden onset, with/without exposure to identified allergen, of skin and/or mucousness with at least 1 of 2:
 1. Respiratory disease (dyspnea, wheezing, stridor, hypoxemia, ...)
 2. HypoTA or Sx associated with a dysfunction of the target organs (hypotonia/collapse, syncope, incontinence, ...)
3. Probable allergen exposure and sudden onset (minutes to hours) of at least 2 of 4:
 1. Skin and/or mucousness (pruritus, rash, hives, etc.)
 2. Respiratory disease (dyspnea, wheezing, stridor, hypoxemia, ...)
 3. HypoTA or associated Sx (hypotonia/collapse, syncope, incontinence, ...)
 4. Persistent GI Sx (abdominal pain, vomiting, ...)
5. Sudden hypotension (minutes to hours) following known allergen exposure
 1. Children: 30% systolic decrease
 2. Adults: 30% decrease vs. basic personal systolic tension

There are no definitive predictors, but various factors of poor prognosis are recognized. These differ slightly between studies, but some seem to return quite systematically in the literature. First, the **severity of the reaction** appears to increase the risk of biphasic reaction. "Severe" means, reactions that initially required **1 dose of epinephrine**, those requiring a higher dose of epinephrine or an intravenous hydration bolus.⁸ Also, patients with **hypotension, pharyngeal edema or severe respiratory distress** upon arrival at the emergency department are among the reactions considered "severe"⁹. Patients with a total duration of **symptoms greater than 30 minutes** also appear to be at greater risk¹⁰. On the other hand, **delayed administration of epinephrine or a late presentation** to the emergency department would also increase the risk of adverse developments.¹¹ Finally, a **history of anaphylaxis** and exposure to an **unknown allergen** would be two additional risk factors for biphasic reaction¹².

It should be noted that most studies dealing with biphasic reactions exclude patients chronically taking corticosteroids, antihistamines, or beta-blockers, as well as patients on immunosuppressants⁶. It is therefore difficult to apply any conclusions to these populations.

1. RELEVANCE

In the current context of increasing emergency department traffic and the introduction of new government, ministerial and institutional requirements to limit emergency room wait times and stretcher time, we believe it is essential to question our practices in order to release patients more quickly and safely by limiting the periods of unreachable observation. Our research team, composed mainly of emergency physicians, hypothesizes that if only one's clinical decision rules remain invalid in the subsequent stages of our project, it is likely that some patients who have had an anaphylactic reaction may be released much earlier than the current conduct. A simple, generalized and valid clinical decision rule would therefore be an interesting asset for the modern practice of emergency medicine.

These rules could also contribute to the satisfaction of patients who would spend less time in the ER. Also, such rules will provide clear guidance to clinicians working in lower-flow settings, where the incidence of anaphylaxis is lower and therefore clinical experience is less sharp. Finally, these rules will be relevant for teaching purposes for the various learners who do internships in our emergency departments.

Our group of emergency medicine clinicians has therefore decided to start a research project to identify the rules of clinical decision following an anaphylaxis in an emergency context. This project was developed in collaboration with the three emergency departments of Saguenay-Lac-St-Jean (Chicoutimi, Jonquière and Alma).

1. STEPS TAKEN

A review of the literature (phase 0; Rapid review) and phase 1 of the project (statistical derivation of two clinical decision rules) have already been completed. The initial "rapid review" literature review was to highlight the main elements that appeared to be predictors of a biphasic reaction. These elements led to the development of an initial clinical decision rule that included 7 variables (Table 1).

Table 1: CLINICAL DECISION RULE ORIGINALLY DEVELOPED FROM THE RAPID REVIEW OF THE LITERATURE

| |
|---|
| 
Promote an observation if one of the following is present:
 
1. Time before the first dose of 60min2. Severe symptoms (hypoTA, respiratory sx, vomiting, intubation, syncope, incontinence)3. Time before symptom resolution - 40 min4. Anaphylaxis ATCD5. Number of doses of EPI IM - 16. Asthma ATCD7. No administration of glucocorticoids |
|---|

Conflicting data in the literature review, a criterion included as exploratory in the "literature-based" rule

However, for the purpose of publishing our Phase 0 (literature review), the analysis of all articles included in the initial literature review (rapid review) was redone by another team member. As a result of this comprehensive review of each article, the literature review has moved from the "rapid review" to the "systematic review" type and minor changes have had to be made to the rule based on the literature review (below).

Table 2: CLINICAL DECISION RULE FROM SYSTEMATIC LITERATURE REVIEW

| |
|---|
| 
Promote an observation if one of the following is present:
 
1. Time before the first dose of 60min2. Severe symptoms (hypoTA, respiratory sx, vomiting, intubation, syncope, arrhythmias, diarrhea)3. Time before symptom resolution - 40 min4. Anaphylaxis ATCD5. Number of doses of EPI IM - 16. Unknown allergen7. No administration of glucocorticoids |
|---|

Conflicting data in the systematic literature review, a criterion included as exploratory in the "literature-based" rule

Thus, in terms of the criterion of severe symptoms of the initial anaphylactic reaction, we added arrhythmias, the presence of diarrhea and we removed incontinence. The asthma history criterion was removed from the rule and we added an unknown allergen.

In Phase 1 of the study, two other clinical decision rules were derived retrospectively. By analyzing the characteristics of patients who had an anaphylactic reaction, we were able to derive a rule to identify a low-risk group of biphasic reaction (any symptom of allergy) and clinically significant biphasic reaction (i.e. meeting the criteria for an anaphylactic reaction). These rules were created with the highest possible negative predictive sensitivities and values (VPNs).

The next step is to prospectively verify whether these rules maintain their sensitivity and negative predictive value with a different sample of patients from the same population pool. The first rule assesses the probability of clinically significant biphasic reactions (sensitivity of 90%, 7 variables; Table 3) and the second, all biphasic reactions (100%, 7 variable sensitivity; Table 4). Areas below the ROC curve were 0.896 and 0.874, respectively. Because the variables selected for each decision-making rule come from a regression model, the predicted probability of a biphasic reaction comes from the linear combination of selected variables. Depending on the coefficients calculated, each variable present in the patient will have a different weight in the decision.

TABLE 3: RETROSPECTIVELY DERIVED CLINICAL DECISION RULE FOR CLINICALLY SIGNIFICANT BIPHASIC REACTIONS

| | |
|----|--|
| 1. | ATCD allergy to a different agent than the one in question |
| 2. | Symptoms of diarrhea |
| 3. | ATCD allergy to the same agent as the one in question |
| 4. | Number of doses of O.R. in the emergency room |
| 5. | Food allergen (other than milk, egg, peanuts, seafood) |
| 6. | Number of doses of O.R. before emergency 1 |
| 7. | ENT symptoms |

TABLE 4: RETROSPECTIVELY DERIVED CLINICAL DECISION RULE FOR BIPHASIC REACTIONS (ALL SEVERITIES CONFUSED)

| | |
|----|---|
| 1. | Number of doses of O.R. in the emergency room |
| 2. | Epi doses data different from standard doses (ped: 0.01mg/kg, adult: 0.3-0.5mg) |
| 3. | Symptoms of diarrhea |
| 4. | ATCD allergy to a different agent than the one in question |
| 5. | Secondary anaphylactic reaction to iodine |
| 6. | Secondary anaphylactic reaction to a sting or bite |
| 7. | Secondary anaphylactic reaction to an unknown allergen |

Note that the first two criteria of the rule for all the combined severity of biphasic reactions (Table 4) were, at the time of diversion, contained in a single criterion: "standard or non-standard doses of IM epinephrine." However, because this criterion contained several pieces of information, it was divided into two new criteria to simplify and clarify data collection. For the first criterion (number of doses of ER in the emergency department), not receiving repeated intramuscular doses of epinephrine decreased the likelihood of having a biphasic reaction. For the second criterion (different doses from standard doses), receiving standard intramuscular doses of epinephrine decreased the likelihood of having a biphasic reaction compared to receiving non-standard intramuscular doses of epinephrine.

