1. METHODOLOGICAL

Based on the three rules of clinical decision (2 derivatives and one based on the literature review), a prospective observational study will be carried out in the emergency departments of Chicoutimi, Jonquière and Alma. Data collection for this theoretical validation phase has been underway since December 2019, having received the approval of the various local research committees (ethics, scientific and convenience).

Inclusion and exclusion criteria

The inclusion criteria will be: all patients of minor or adult age who have had anaphylaxis that meet the known diagnostic criteria. In addition, if a patient presents with confirmed exposure to an allergen and symptoms that do not yet meet the anaphylaxis criteria, they may be included in the study. This will only be possible if the doctor deems that he will inevitably progress to anaphylaxis and treat him in this way. Those who have had a reaction to taking a drug (e.g. IECA), who are known for a hereditary pathology (hereditary angioedema), immune OR other pathology giving an anaphylactoid reaction will be excluded, as in Phase 1 of the study.

Sample size

The required sample size was adjusted for the primary objective based primarily on the study of sensitivity and specificity. As a low prevalence of biphasic reactions is expected, a calculation based on specificity is useless, therefore to be rejected. Thus, using the statistician involved in the study and using a sample size calculation adapted for a confidence interval on a ratio adjusted according to the Buderer¹³ formula, it was determined that it was necessary to have 553 patients in total to estimate a sensitivity of at least 98% with a confidence level of 95% according to an accuracy of 5% and an expected prevalence of 6%. Note that a 10% rate was added to the initial size calculation to manage the possibility of missing data. The prevalence of 6% was determined from the prevalence of biphasic reactions observed when collecting Phase 1 data from the same study..

Data collection

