13. Syed Mustansir Hussain Zaidi et Al., Sample size estimation of diagnostic test studies in health sciences, *Proc. 14th International Conference on Statistical Sciences*, Karachi, Pakistan, March 14-16, 2016, Vol. 29, pp. 239-246.

1. APPENDIX: QUESTIONNAIRE SHARED - Phase 2 study (validation)

To be filled for any patient with an anaphylactic reaction AFTER initial management but BEFORE discharge

Site of the visit: Chicoutimi Jonquière Alma

Date : _____

Time of arrival in the emergency room:

The time at which this questionnaire is completed:

| | |
|--|--|
| The patient meets the criteria for an anaphylactic reaction: yes no   | If answered no to the last question: the patient confirms exposure to an allergen and I believe that it will inevitably evolve towards an anaphylactic reaction. yes no   |
|--|--|

Time of onset of symptoms:

Exact time: - **ESTIMATED** time:

Hours of cob doses:

1^{is} _____, 2,^{and} _____, 3,^{and} _____, 4,^{and} _____, 5^{and} _____, 6,^{and} _____

History

ATCD allergy to an allergen other than the one involved. yes no

ATCD of allergy to the allergen involved. yes no

ANaphylaxis ATCD. yes no

Asthma ATCD. yes no

Allergen

Insect bite or bite. yes no

Iodine. yes no

Unknown allergen. yes no

Food allergen other than milk/peanuts/eggs/seafood. yes no

Symptoms

Severe symptoms (hypoTA, respiratory sx, vomiting, intubation, syncope, arrhythmias). yes no

ENT symptoms. yes no

Diarrhea. yes no

Time before symptom resolution - 40 minutes. yes no

Treatment

Time before the first dose of ear - 60 minutes. yes no

Number of doses of epi IM - 1. yes no

Number of ear doses before emergency room arrival. yes no

Number of ear doses in the emergency room. yes no

Epi doses data different from standard doses (ped: 0.01mg/kg, adult: 0.3-0.5mg). yes no

Administration of glucocorticoids. yes no

Section reserved for investigators

Rb. yes no

RBCS. oui non

[name]. yes no

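### The severe-symptoms item of the Table 2 rule largely repeats the Box 1 entry criteria, so its sensitivity is likely inflated by a high flagged share, and no decision step corrects for that

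*Combined protocol and SAP*

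**What the plan says.** The literature rule in Table 2 (Steps taken) opens with "Promote an observation if one of the following is present", so one positive item is enough. Item 2 is "Severe symptoms (hypoTA, respiratory sx, vomiting, intubation, syncope, arrhythmias, diarrhea". Neither the table nor the text around it grades these signs.

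Eligibility (Methodological, inclusion criteria) covers "all patients of minor or adult age who have had anaphylaxis that meet the known diagnostic criteria". It also admits patients who do not yet meet the criteria but whom the physician expects to progress. Box 1 (Problem) builds the diagnosis from skin or mucosal signs, "Respiratory disease (dyspnea, wheezing, stridor, hypoxemia" and similar, "HypoTA or associated Sx (hypotonia/collapse, syncope, incontinence" and similar, and "Persistent GI Sx (abdominal pain, vomiting" and similar. Its third criterion is sudden hypotension after known exposure.

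The Problem section elsewhere describes severe presentations more narrowly: "hypotension, pharyngeal edema or severe respiratory distress". The questionnaire in the appendix collects the item as a single box, "Severe symptoms (hypoTA, respiratory sx, vomiting, intubation, syncope, arrhythmias). yes no". Diarrhea has its own box there.

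On decisions, Data analysis plans sensitivity, specificity and both predictive values with confidence intervals, and chooses the best derived rule on sensitivity. Phase 1 and 2 data are pooled for re-derivation only if no rule keeps a high enough sensitivity and/or negative predictive value. Potential outcomes judges effectiveness on sensitivity and negative predictive value and, if several rules succeed, takes the one easiest to apply. No minimum specificity or minimum share released is set anywhere.

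**The concern.** A rule meant to find low-risk patients has to separate patients within the enrolled cohort. When one sufficient item restates the conditions for entering that cohort, the rule is positive for many patients simply because they were enrolled. Its sensitivity then rises with the share flagged, whether or not the items predict a biphasic reaction.

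The study's purpose is earlier safe release. If sensitivity and negative predictive value decide, a rule that releases very few patients can pass, win the ease-of-use tie-break over the regression-weighted rules, or prevent the re-derivation that the plan keeps in reserve.

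**Working it through.** **1. The plan's own figure.** The inputs in Sample size are sensitivity 98%, precision 5%, confidence 95%, prevalence 6% and a 10% allowance. Buderer: 1.96² × 0.98 × 0.02 / 0.05² = 30.1 events; 30.1 / 0.06 = 502 patients; 502 × 1.10 = 552.2, rounded up to 553. The figure reproduces. Expected events are 553 × 0.06 ≈ 33.

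**2. Item 2 against Box 1.**

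| Box 1 route | Item 2 under the literal wording |
|---|---|
| First: skin + respiratory | positive |
| First: skin + hypotension or associated signs | positive if hypotension or syncope; negative if only hypotonia/collapse or incontinence |
| Second: six two-system pairs | five contain the respiratory or the hypotensive component; the sixth, skin + GI, is positive if the GI sign is vomiting or diarrhea |
| Third: hypotension | positive |

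Take nine signs: skin, respiratory, hypotension, syncope, hypotonia/collapse, incontinence, abdominal pain, vomiting, diarrhea (diarrhea counted as GI). Of the 2⁹ = 512 patterns, 495 meet Box 1, and 485 of those (98%) are item-2 positive. The 10 that escape contain only skin, abdominal pain, hypotonia/collapse and/or incontinence. This counts patterns, not patients. It locates the overlap but does not estimate a flagged share.

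**3. Size, under an assumption.** Let e be the share of patients who are item-2 negative, and q the share of those with at least one of the other six items. The flagged share is f = 1 − e(1 − q). The documents give neither e nor q.

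- e = 5%: item 2 alone flags 95%, leaving 553 × 0.05 ≈ 28 patients unflagged.
- e = 15%: item 2 alone flags 85%, leaving 553 × 0.15 ≈ 83.
- Adding the other items with q from 0 to 0.9: e = 2% gives f of 98.0% to 99.8%; e = 5% gives 95% to 99.5%; e = 20% gives 80% to 98%.

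**4. What an uninformative rule would show.** A rule unrelated to outcome that flags a share f has expected sensitivity f and specificity 1 − f. With 33 events:

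| f | Chance of 33/33 (f³³) | Chance of at least 32/33 | Released, of 553 |
|---|---|---|---|
| 0.90 | 0.03 | 0.14 | about 55 |
| 0.95 | 0.18 | 0.50 | about 28 |
| 0.98 | 0.51 | 0.86 | about 11 |
| 0.99 | 0.72 | 0.96 | about 6 |

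Whenever all 33 are caught, the observed negative predictive value is also 100%, so that measure gives no protection by itself.

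**5. Would a check against the flagged share catch this?** Take f = 0.98 with 33/33 caught and 11 of the 553 − 33 = 520 patients without a reaction released. Sensitivity + specificity − 1 = 1 + 11/520 − 1 = 0.021. The exact lower 95% limit for 33/33 is 0.025^(1/33) = 0.894. Holding specificity at 0.021, this gives 0.894 + 0.021 − 1 = −0.085, so the interval covers 0 and the rule is not called effective. A simple normal-approximation interval would fail here: it gives sensitivity no variance at 33/33 and runs 0.021 ± 1.96 × √(0.021 × 0.979 / 520), about 0.009 to 0.034. The interval method must therefore be named.

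**The case against.** A reader might infer that the rule flags almost every enrolled patient and that its sensitivity is near 100% by construction. The documents do not support that. They give no symptom frequencies, the 485 of 495 is a count of patterns, and the assumed 85% to 95% for item 2 alone lies below the plan's 98% target. The other six items raise it by an unknown amount. Patients enrolled before meeting the criteria may also be item-2 negative, in an unstated share.

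The item is headed as severe symptoms, so a physician may read the heading as grading each sign and answer no for mild dyspnea. Nothing rules this out. If it happens, the overlap shrinks, but the item then depends on each physician's own threshold. That too is a defect of definition.

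Specificity is to be reported, so a rule with little separation would be visible. That is correct, but no decision step uses it. The sentence that selects on sensitivity speaks of the best derived rule, which may cover only Tables 3 and 4. Goals and assumptions and Potential outcomes, however, speak of the rules generally, so the literature rule remains open to being called effective. No rule is applied to patients in this phase, which limits immediate harm but not the choice of rule for Phase 3.

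A reader might also infer that the components can never be separated. Diarrhea already has its own box, and the others may be in the charts. The planned file review covers outcomes only, though, so extracting components would be new work, and work exposed to knowledge of the outcome.

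**Conclusion.** The point holds as a structural one: item 2, read literally, largely duplicates eligibility, one positive item is enough, and the criteria for success do not use specificity or the share released. The Table 2 rule's sensitivity is therefore likely to be inflated by a high flagged share.

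Confidence is high for the overlap and for the gap in the decision criteria, and low for the magnitude. The 85% to 95% for item 2 alone rests on the assumed 5% to 15% item-2-negative share and on the ungraded reading. The 0.51 chance of a perfect result applies only if the whole rule flags 98% and carries no information; at 90% flagged it is 0.03. Whether the literature rule carries information beyond its flagged share is left open by the documents. The plan should be able to tell, and as written its decision criteria cannot.

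**What to change.** 1. Keep the Table 2 rule and score it as printed, combining the composite box with the separate diarrhea box.
2. In Data analysis and Potential outcomes, report for all three rules the share of patients released and the specificity, with confidence intervals, beside sensitivity and negative predictive value. Pre-specify that a rule is called effective, or counts against re-derivation, only if its sensitivity exceeds its false-positive rate: the 95% interval for sensitivity + specificity − 1 must lie above 0. Use an interval that remains valid at 100% sensitivity, such as one built from Wilson limits. State whether the selection sentence covers the literature rule.
3. From now on, replace the composite questionnaire box with one box per component. Reconcile Table 2 with the description of severe reactions in the Problem section, and state on the form whether the heading grades each sign. Report the item-2-negative share among patients who meet the criteria.
4. Label any rescoring with a narrower item 2 as exploratory, since it tests a different rule. If components of earlier forms are filled from charts, use initial-visit notes only, abstracted without knowledge of the biphasic outcome, and analyse by form version.

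The cost is a slightly longer form, two form versions in one dataset (collection began in December 2019), optional extra chart abstraction, and possibly a less favourable reading of the literature rule. Patient care and the sample size do not change.

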In the face of a case of anaphylaxis, the doctor will have to answer a short questionnaire developed with the variables present in each of the three rules (questionnaire available in appendix). The variables were randomly arranged on the questionnaire so that no rules could be recognized or inferred. If the doctor deems that a patient who does not yet present the anaphylaxis criteria, but in the absence of ahead, will eventually progress to real anaphylaxis, he or she will have to indicate it at the appropriate location on the questionnaire. Indeed, as mentioned above, these patients will be included in the study, but we will independently analyze the results of this sample to determine if they are different from the overall results in subgroup analyses.

The questionnaire will be available at several key locations, including in the paper-based resuscitation rooms in the three emergencies where data collection will take place. The questionnaire will also be systematically placed on the file of patients with suspected anaphylaxis at triage. The doctor will be required to complete the questionnaire anonymously, but will be required to provide the patient's file number. This will be done after the initial stabilization. After completing the questionnaire, the physician will simply be able to continue to care for the patient as he would have done in accord with his standard clinical practice. No decision rules will be applied to patients. The answers provided to

the questionnaire will therefore have no impact on the clinical decisions made by the treating physician. The research team will then review each of these files to assess whether or not there was a biphasic reaction and whether it was clinically significant (according to the NIAID/FAAN²criteria).

At the next emergency department meetings involved, doctors will be notified of the operation of the current study. Recalls will be made as required during the course of the study to ensure the involvement of the medical profession. Administrative officers and triage nurses will also be advised to add the questionnaire to all potential anaphylaxis files.

Data analysis

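### On the clinically significant outcome alone, a recurrence treated with epinephrine before it meets NIAID/FAAN is a non-event, so NPV for release without observation is unchanged or too favourable

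*Combined protocol and SAP*

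**What the plan says.** Steps Taken describes two Phase 1 outcomes. One is wide: a rule was derived to find a "low-risk group of biphasic reaction (any symptom of allergy" recurrence. The other is narrow: a "clinically significant biphasic reaction (i.e. meeting the criteria for an anaphylactic reaction". The Table 3 rule was derived for the narrow outcome (sensitivity 90%) and the Table 4 rule for the wide one (100%).

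Methodological, Data collection, carries both into Phase 2. The research team will "review each of these files to assess whether or not there was a biphasic reaction and whether it was clinically significant", judged by NIAID/FAAN. The Appendix form has separate investigator boxes for any biphasic reaction (Rb) and for the clinically significant kind (RBCS). Nothing in the narrow definition refers to treatment.

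No rule is applied to patients. After completing the form, "the physician will simply be able to continue to care for the patient as he would have done".

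For the index reaction, the plan does foresee treatment before full criteria. Patients with confirmed exposure and "symptoms that do not yet meet the anaphylaxis criteria, they may be included in the study", with the condition: "This will only be possible if the doctor deems that he will inevitably progress to anaphylaxis and treat him in this way". They are flagged on the form, and "we will independently analyze the results of this sample to determine if they are different from the overall results in subgroup analyses". Recurrences have no comparable provision.

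**The concern.** The project asks whether some patients can safely leave without prolonged observation (Relevance; Potential Outcomes). The narrow outcome is measured while that observation, and the treatment it allows, are in place. A recurrence noticed early and given epinephrine may never reach NIAID/FAAN, and is then coded RBCS = no. Had the rule been followed, a rule-negative patient would have been sent home without that observed treatment.

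Sensitivity and NPV decide whether a rule goes to Phase 3 (Data analysis; Potential Outcomes). If some rule-negative patients had recurrences contained by treatment, the narrow outcome credits the rule for avoiding a harm that observation may have prevented. The wide outcome cannot settle this, because it does not separate these recurrences from trivial allergy symptoms.

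**Working it through.** **Expected events.** Inputs from Methodological, Sample size: sensitivity 0.98, 95% confidence, precision 0.05, prevalence 0.06.

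n = 1.96² × 0.98 × 0.02 / (0.05² × 0.06) = 501.95, so 502. Then 502 × 1.10 = 552.2, so 553, as stated.

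The 6% covers biphasic reactions without restriction to significant ones. Expected events of any severity are 502 × 0.06 ≈ 30. The clinically significant subset can be no larger; its size is not given.

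**How an early-treated, sub-criteria recurrence is scored**

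| Rule result | Narrow outcome (RBCS) | Wide outcome (Rb) |
|---|---|---|
| Negative (discharge) | true negative | false negative |
| Positive (observe) | false positive | true positive |

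**Direction.** Let E be coded significant events, TP those flagged, K early-treated recurrences, u those of K that the rule misses, and N the number of rule-negatives. Counting the K cases as events gives:

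- Sensitivity = (TP + K − u) / (E + K). It falls only if u/K > (E − TP)/E, that is, if the rule misses these cases more often than coded events.
- NPV = 1 − (E − TP + u)/N. It can only stay the same or fall.

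**Illustration 1.** Assumed: E = 15, TP = 14, K = 4, N = 250. As coded, sensitivity is 14/15 = 93.3% (exact 95% CI 68.1 to 99.8) and NPV is 249/250 = 99.6%.

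| Missed among the 4 | Sensitivity | NPV |
|---|---|---|
| 0 | 18/19 = 94.7% | 249/250 = 99.6% |
| 1 | 17/19 = 89.5% | 248/250 = 99.2% |
| 2 | 16/19 = 84.2% | 247/250 = 98.8% |
| 4 | 14/19 = 73.7% | 245/250 = 98.0% |

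**Illustration 2.** Assumed: 30 biphasic reactions, 10 to 20 of them significant, coded sensitivity 90%, and 10% to 50% of the remaining recurrences treated early. Sensitivity on the wider event is:

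- 0.90 (unchanged) if the rule misses 10% of the early-treated cases;
- 0.80 to 0.89 if it misses 30%;
- 0.70 to 0.88 if it misses 50%.

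A single missed case moves 9/10 (90%) to 9/11 (82%), or 18/20 (90%) to 18/21 (86%).

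**The case against.** Three stronger readings are tempting, and the documents support none of them.

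- **A reader might infer that these recurrences are scored as safe releases throughout.** They are not. On the wide outcome a rule-negative patient of this kind is a miss. That outcome is closer to the stated hypothesis and is the source of the 6%.
- **A reader might infer that the plan contradicts itself by counting an equally early index reaction as anaphylaxis.** It does not. That provision is a conditional eligibility rule that requires confirmed exposure, with a flag and a subgroup analysis. It does not define an outcome, and a biphasic reaction by definition involves no new exposure.
- **A reader might infer that sensitivity is inflated.** The direction is open: 18/19 exceeds 14/15. Flagged cases currently count as false positives, which penalises specificity and PPV.

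Other objections carry weight. Every count above is assumed, and few recurrences may be involved: after probable exposure, NIAID/FAAN needs only two of four systems. Even 73.7% lies within the interval around 14/15, although that interval reflects sampling error and does not remove a systematic shift. The Phase 1 definition is needed to test whether the 90% is maintained. Phase 3 would follow every patient to whom the rule is applied, but Phase 2 results decide which rule gets there.

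The best objection is to a careless remedy. Epinephrine dose counts are predictors in Tables 2, 3 and 4, and the form may be completed at any time up to discharge. A dose given for a recurrence could enter the predictor; if it also defined the event, sensitivity would be inflated by circularity.

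One investigator field on the form is removed from the public text, so what it records is unknown.

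**Conclusion.** The point holds for the clinically significant outcome only. Under usual care, its NPV is unchanged or too favourable as a guide to release without observation. Its sensitivity is too favourable only if early-treated recurrences are missed more often than coded events. The size cannot be derived from the documents. With at most about 30 biphasic reactions expected, a few such cases could move sensitivity by several points; in the first illustration NPV moves by at most 1.6 points.

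This rests on two assumptions: that some recurrences are given epinephrine below criteria, and that some of those patients are rule-negative. Not all of these recurrences would have progressed untreated, so the wider event gives a cautious comparison and not a corrected estimate. The point is a cheap improvement to what Phase 2 can say about safe release. It does not invalidate the design or the sample size.

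**What to change.** 1. **File review (Data collection; Data analysis).** Record whether epinephrine was given for the recurrence and whether NIAID/FAAN was met by then.
2. **Main analysis.** Keep the Phase 1 definition, so that the 90% can still be compared.
3. **Sensitivity analysis.** Prespecify sensitivity and NPV, with confidence intervals, for each rule, with the event defined as meeting NIAID/FAAN or treated with epinephrine.
4. **Predictors.** Use the dose times on the form to exclude doses given for the recurrence from the epinephrine counts in Tables 2, 3 and 4. The translated labels are garbled; I read these fields as epinephrine doses.
5. **Use.** Report the result beside the main one when judging whether a rule is safe enough for Phase 3. It need not be a separate pass/fail gate.

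The cost is one or two fields in a review already planned and one extra row per rule. The wider event depends partly on physicians' treatment thresholds and differs from the Phase 1 outcome. The figures may also be less favourable.
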